 the baseline visit. The CGM device will be placed, so the patient will know how to do this at
 home. The placement of the CGM, as well as the first CGM reading, will be done prior to
 administration of the first dose of study drug(s). The Sponsor will supply the CGM devices.
- **Tuberculosis test:** As part of the eligibility verification, all patients will undergo a test to determine whether the patient shows signs of active or latent tuberculosis. The decision on the type of test to be used is left to the discretion of the investigator, and could include e.g. TST, TSPOT, QuantiFeron or other appropriate tests.
- Concomitant medications: At every visit, the investigator will obtain information about concomitant medications the patient is taking (including dose, frequency, route of administration, start and stop dates)

6.2.Safety Assessments

Safety will be assessed by collecting and recording Adverse Events (AEs) and laboratory assessments and the presence of *L. lactis* sAGX0407 in whole blood.

The study will utilize local laboratories for safety assessments. The clinical laboratory will indicate laboratory values out of normal ranges. The Investigator must assess all abnormal clinical laboratory results for clinical significance in a timely fashion. A notation of 'clinically significant' (CS) or 'non-clinically significant' (NCS) with initials and date will be documented on the respective laboratory report next to any abnormal value. An abnormal clinical laboratory value will be considered and documented as an AE, if in the opinion of the Investigator, it is clinically significant. The Investigator will follow proper adverse event reporting procedures.

For details on the data to be collected for adverse events, please refer to Section 8.

XXX

6.3.Laboratory Assessments

6.3.1General considerations

Throughout the study, blood samples will be collected at regular intervals, as described in the Visit schedule

XXX

Confidentiality Statement

XXX

6.3.2Local lab assessments

Parameters to be analysed will include:

- Hematology: complete blood count: Red Blood Cell (RBC) count, haemoglobin, haematocrit, mean corpuscular volume (MCV), mean corpuscular haemoglobin (MCH), mean corpuscular haemoglobin concentration (MCHC), RBC distribution width (RDW), white blood cell (WBC) count, differential count, platelet count
- Serum Chemistry: blood glucose, sodium, potassium, chloride, calcium, CO₂/bicarbonate

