10.7. Safety Analysis

Safety will be assessed based on TEAEs, physical examination findings, vital sign measurements and clinical laboratory tests.

Adverse events will be coded to a Medical Dictionary for Regulatory Activities (MedDRA) preferred term and system organ classification. The occurrence of treatment emergent AEs will be summarized by treatment frequency received using preferred terms, system organ classifications and severity. If a patient experiences multiple events that map to a single preferred term, the greatest severity and/or strongest investigator assessment of relation to study drug will be assigned to the preferred term for the appropriate summaries. Separate summaries of treatment emergent SAEs and treatment emergent AEs that are related to either IMP will be generated. Summaries may be repeated according to study phase. All AEs will be listed for individual patients showing both verbatim and preferred terms.

Descriptive summaries of vital signs and quantitative clinical laboratory changes will be presented by treatment received and study visit. The number and percentage of patients experiencing laboratory abnormalities and clinically relevant laboratory abnormalities will be summarized by treatment received. Cross tabulations of baseline abnormality vs. worst post treatment abnormality for selected laboratory assessments will presented by treatment received.

Abnormal physical examination findings will be presented by treatment received. The number and percentage of patients experiencing each abnormal physical examination finding will be included.

Prior and concomitant medications will be coded using the World Health Organization (WHO) dictionary. These data will be listed.

The number and percentage of patients with presence of sAGX0407 bacteria will be summarized by treatment group.

10.8.Interim Analysis

Interim analyses will be performed according to the below schedule:

After the last Day 180 follow-up visit of the last patient enrolled into the Phase 1b portion of
the study, a preliminary analysis of the data collected up to 6 months will be performed for
these patients.

Confidentiality Statement

- Once all patients enrolled in Combination Cohort 1, as well as the 2 patients enrolled into the
 open label portion of Combination Cohort 2, have completed the Day 180 follow-up visit,
 unblinding will be done and an interim analysis will be performed.

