11.4.3.5.1 Temporary interruption of teplizumab infusions

If any of the following lab abnormalities is observed (normal range per local lab reference ranges), the test may be repeated on the same day. If the repeated test result normalizes, that day's dose may be given. If the value is still in the indicated range or worsens, or if the test cannot be repeated on the same day, that day's dose should be withheld.

XXX

If the above event(s) resolve(s) within 2 days, study drug dosing may be resumed according to the original schedule. The treatment course will not be extended beyond 12 days.

If the above events do not resolve after 2 consecutive days of interruption, the Medical Monitor must be consulted regarding continuation of study drug dosing.

11.4.3.5.2Permanent discontinuation of teplizumab infusions

The following situations, laboratory abnormalities, or adverse events will lead to permanent discontinuation of infusions *during the treatment course*: (Note: Day 1 is the first day of infusion)

XXX

Confidentiality Statement

11.4.3.6Further Evaluation after Withholding Teplizumab Infusions

The following are minimal assessments to be performed for those participants in whom an infusion is withheld (as described above):

XXX

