6.1 Changes in the Planned Analyses

There has been no changes to the planned analyses.

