In addition to the above lab assessments to be analysed by the site's local lab, EBV/CMV/HCV/HBV/HIV monitoring assessments will be done. These measurements were performed at screening for all patients and at Visit 13-16, Visit 19 for repeat dose patients. Potential reactivation will be assessed at regular intervals by polymerase chain reaction (PCR) for viral load.

For hematology, clinical chemistry, liver function, coagulation parameters and CRP summary statistics will be produced for observed values. In addition, the difference from baseline to each visit at which they were assessed will be derived and presented.

Shift tables showing the number of subjects who changed from normal, abnormal not clinical significant or abnormal clinical significant at baseline to normal, abnormal not clinical significant or abnormal clinical significant at each post-baseline time of assessment will be presented.

Figures showing mean and median values over time per cohort will be shown for CRP, AST and lymphocytes.

Number of patients with positive/negative serology at baseline and positive/negative for PCR per visit will be tabulated.

All laboratory parameters will be listed. Abnormal values will be flagged in listings.

In addition, all study patients (except for the single dose patients) will receive a XXX continuous glucose monitor (CGM) device for the entire duration of their study participation. The data generated by the device will be downloaded at every site visit. The devices will store data for up to 30 days. The device measures glucose every 5 minutes, thus every measurement will be said to have a duration of 5 minutes when the calculation of total duration is performed. The first measurement is said to measure the glucose value 5 minutes before the actual measurement. For the CGM data collected at each visit:

- The total CGM recording time,
- Time in range (the time greater than or equal to 71 mg/dl and less than or equal to 179 mg/dl),
- Time above range (the time above 179 mg/dl),
- Time in the low range (the time below 71 mg/dl),
- Time in the very low range (the time below 50 mg/dl) and
- Time with missing values

will be summarized in hours/minutes and percentages of the total CGM recording time, per cohort.

Physical Examination

The physical examination included visual inspection of skin, examination of eyes, ears and throat, auscultation of heart, lungs and abdomen, and percussion/palpation of abdomen. The results will be recorded as

- Normal,

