14.3 SAFETY DATA

(Safety presentations will be based on the safety set unless otherwise stated below)

- 14.3.1.x Summary of All Adverse Events for single dose AG019 patients
- 14.3.1.x Summary of All Adverse Events for repeat dose AG019 patients
- 14.3.1.x Summary of All Adverse Events for combination cohort patients
- 14.3.1.x All Adverse Events by System Organ Class and Preferred Term
- 14.3.1.x Treatment-Emergent Adverse Events by System Organ Class and Preferred Term
- 14.3.1.x Treatment-Emergent Adverse Events by System Organ Class and Preferred Term during AG019 treatment period
- 14.3.1.x Treatment-Emergent Adverse Events by Severity, System Organ Class and Preferred Term
- 14.3.1.x Treatment-Emergent Adverse Events by Severity, System Organ Class and Preferred Term during AG019 treatment period
- 14.3.1.x Treatment-Emergent Adverse Events by Relationship to AG019, System Organ Class and Preferred Term
- 14.3.1.x Treatment-Emergent Adverse Events by Relationship to AG019, System Organ Class and Preferred Term during AG019 treatment period

14.3.1.x Treatment-Emergent Serious Adverse Events by System Organ Class and Preferred Term

14.3.1.x Treatment-Emergent Adverse Events Leading to Premature AG019 Treatment Discontinuation by System Organ Class and Preferred Term

14.3.4.x Laboratory Measurements:
Summary Statistics by Visit with Difference from Baseline (Hematology & INR, Clinical Chemistry, Liver Function & CRP and HbA1c)
Shift Tables (Hematology & INR, Clinical Chemistry, Liver Function & CRP)
Figures of mean and median CRP, AST and Lymphocytes over time
Number of patients with positive/negative serology at baseline and positive/negative for PCR per visit
Summary of CGM Recording Time

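### The SAP omits, without declaring it, the protocol's two patient-level laboratory summaries (any abnormality; baseline versus worst value), and its by-visit shift tables cannot replace them for repeat-dose and combination patients

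*SAP*

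**What the plan says.** Protocol 10.7 commits to two displays by treatment received. The first is a patient count: "The number and percentage of patients experiencing laboratory abnormalities and clinically relevant laboratory abnormalities will be summarized by treatment received". The second compares each patient's baseline with the worst later result: "Cross tabulations of baseline abnormality vs. worst post treatment abnormality for selected laboratory assessments will presented by treatment received".

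SAP 6.3.9 plans, for local laboratory values, summary statistics and differences from baseline by visit, figures of mean and median CRP, AST and lymphocytes, and shift tables from the baseline category (normal, abnormal not clinically significant, abnormal clinically significant). The shift-table sentence ends "abnormal not clinical significant or abnormal clinical significant at each post-baseline time of assessment will be presented". It adds a listing: "All laboratory parameters will be listed. Abnormal values will be flagged in listings".

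The matching entry in the SAP 7.1 output list is "Shift Tables (Hematology & INR, Clinical Chemistry, Liver Function & CRP". No count of patients with any abnormality and no worst-value table is listed.

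SAP 6.1 states: "There has been no changes to the planned analyses".

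**The concern.** Safety and tolerability are the primary objective. For laboratory data, a natural question is how many patients in each group became abnormal at any time, and how far from where they started. The two displays in Protocol 10.7 answer that. A shift table for each visit answers a different question: how many patients are abnormal on that day.

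The difference matters most in the combination cohorts, where blood is checked before each of 12 daily infusions. Short-lived changes in blood counts, liver tests or INR in different patients on different days are spread over many tables, each with a small count. The tables do not say whether the same patient or different patients are involved.

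The omission is also undeclared. Protocol 10.9 has the study report describe deviations from the SAP. A display that the SAP itself leaves out is not a deviation from the SAP, so by that rule it need not be mentioned.

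**Working it through.** The plan states no figure to reproduce, so the check is a comparison of texts followed by a bound.

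**1. Is this analysis someone else's task, or based on an older protocol?** No. SAP 1 hands PK, MMTT, immune markers and mechanistic assessments to others. SAP 3.2 keeps laboratory variables as secondary safety endpoints within the SAP. SAP 1 names protocol Version 9, the current one, as its basis.

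**2. The texts side by side**

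| Display | Protocol 10.7 | SAP 6.3.9 | SAP section 7 |
|---|---|---|---|
| Patients with any abnormality and any clinically relevant one, n (%) | planned | absent | absent |
| Baseline versus worst post-treatment, selected tests | planned | absent | absent |
| Baseline versus each post-baseline time | not named | planned | shift tables (7.1) |
| Descriptive statistics and changes by visit | planned | planned | planned (7.1) |
| Listing of values | not named | planned, with flags | planned (7.2) |

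The output list says only that shift tables will be made, but SAP 6.3.9 defines them as one comparison per post-baseline time. They cannot be read as including a worst-value table.

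**3. Scheduled post-baseline draws (Protocol 7.2 and 7.3)**

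- AG019 repeat-dose: Days 4, 7, 12, 28, 56, 90, 180, 270 and 360, so 9.
- Combination: these 9 plus Days 2, 3, 5, 6, 8, 9, 10 and 11, so 9 + 8 = 17.
- INR is not named in the visit lists after Day 12. That leaves Days 2 to 12, 11 draws, in the combination cohorts and Days 4, 7 and 12, 3 draws, in the AG019 cohorts.
- Single-dose: Day 4 only, so 1.

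From Day 28 the visit lists name hematology and chemistry. Whether that includes the liver tests depends on Appendix A, which is not in the available text, so the counts of 9 and 17 are firm only for the blood count.

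**4. Group sizes.** In each combination cohort, 2 open-label patients plus 10 × 4/5 = 8 randomized patients give 10 active; 10 × 1/5 = 2 are on placebo. AG019 cohorts have 4 to 6 repeat-dose patients and 2 single-dose patients.

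**5. What by-visit counts determine.** Suppose all n patients are normal at baseline and sampled each time, and each of V tables shows k abnormal patients. The number ever abnormal then lies between k (always the same patients) and min(n, k × V). With k = 1:

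| Group | n | V | Ever abnormal |
|---|---|---|---|
| Combination active, blood count | 10 | 17 | 1 to min(10, 17) = 10 (10% to 100%) |
| Combination active, INR | 10 | 11 | 1 to min(10, 11) = 10 (10% to 100%) |
| AG019 repeat-dose, blood count | 6 | 9 | 1 to 6 (17% to 100%) |
| AG019 repeat-dose, blood count | 4 | 9 | 1 to 4 (25% to 100%) |
| AG019 repeat-dose, INR | 6 | 3 | 1 to 3 (17% to 50%) |
| AG019 repeat-dose, INR | 4 | 3 | 1 to 3 (25% to 75%) |
| Single-dose | 2 | 1 | exactly 1 (50%) |

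The bound uses no assumed event rate. For single-dose patients the by-visit and worst-value tables are the same table when only scheduled draws are used.

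**The case against.** The case for leaving the SAP alone has substance.

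- **Clinically significant values are counted elsewhere.** Protocol 6.2 says: "An abnormal clinical laboratory value will be considered and documented as an AE, if in the opinion of the Investigator, it is clinically significant". Those arising on treatment enter the TEAE tables, which count patients by preferred term across all visits (SAP 6.3.8). Protocol 8.6 also makes certain prolonged or late lymphopenias reportable as SAEs. This stands, and it narrows the gap. It does not cover abnormal values judged not clinically significant, and it gives no baseline-versus-worst comparison.
- **The data remain visible.** Every value is listed with abnormal ones flagged, and by-visit statistics include minimum and maximum (SAP 6.3.2). In cohorts this small, a reader could count patients by hand. This stands too: what is missing is the summary, not the information.
- **The study is descriptive.** No test, significance level or sample size depends on these tables, and the primary endpoint, TEAE incidence, is untouched. Correct.
- **Protocol section 10 calls itself brief and leaves detail to the SAP.** That allows the SAP to choose the selected tests. It does not make two named displays optional, nor does it make the no-change statement in SAP 6.1 true.

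Three stronger readings are tempting and are not supported.

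- A reader might infer that abnormal results are lost when a repeat is normal, because before an infusion "the test may be repeated on the same day" (Protocol 11.4.3.5.1). The SAP does not say that a repeat replaces the first value or that unscheduled values are excluded. It is silent on both, and all values are listed.
- A reader might compound an assumed abnormality rate over the daily draws to get a share ever abnormal. The documents give no such rate, and consecutive days in one patient are unlikely to be independent.
- A reader might take CTCAE grading of laboratory values as part of the omitted analysis. Protocol 10.7 does not ask for it.

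**Conclusion.** The point holds as a gap in the summary tables and an inaccurate statement in SAP 6.1. Two displays promised in Protocol 10.7 are missing from the SAP text and its output list, and the by-visit shift tables do not substitute for them in repeat-dose and combination patients. In a combination cohort, one abnormal patient at every visit is compatible with 1/10 to 10/10 active patients ever abnormal.

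The loss falls mainly on abnormal values judged not clinically significant and on the baseline-versus-worst comparison. It does not support a claim that the share ever abnormal cannot be found: it can be derived from the listings, and clinically significant values have their own route through the adverse event tables. Single-dose patients are unaffected on scheduled draws.

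The conclusion rests on the documents' wording, the visit schedule in Protocol section 7 and the planned group sizes. The change should be made because safety is the primary objective and the remedy is cheap. It is not a threat to the primary analysis.

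**What to change.** In SAP 6.3.9 and the 7.1 output list, add per treatment group:

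1. A table of baseline category against worst post-baseline category, in the existing three categories (normal, abnormal not clinically significant, abnormal clinically significant), for named tests. The tests checked before each infusion are a natural choice: CBC, AST, ALT, LDH, total bilirubin and INR. The protocol says only that tests will be selected, so the SAP has to name them.
2. The number and percentage of patients with any abnormal and with any clinically significant post-baseline value.

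State that unscheduled and repeat values count towards the worst value. Protocol 10.7 is silent on this, so it is a new rule to be written down and not a restoration. Keep the by-visit shift tables as support. Correct SAP 6.1; if the sponsor prefers to omit either display, declare and justify that there. CTCAE grading of laboratory values is an optional addition.

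The cost is SAP wording and a few programmed tables from data already collected. No new sampling is needed.

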6.4.1 Electronic Patient Reported Outcomes (ePRO)

All patients (except for the single dose patients) will be asked to keep an electronic diary. The diaries will contain following information:

Confidentiality Statement

- Safety related information (all experienced adverse events and serious adverse events, including signs of clinical sepsis and known risks associated with the use of anti-CD3 mAb or with T1D glycemic control)
- Occurrence of hypoglycemic events including all relevant information for standard classification (these will be captured separately from other safety related information)
- Deviations from planned study drug intake (e.g. missed doses or incorrect doses taken)
- Changes in concomitant medication intake
- Insulin requirements: Daily

The electronic diaries will be kept from the day of signing the informed consent until the patient is withdrawn or completes the study.

A site research coordinator will train the patients on how to complete the electronic diary.

The research coordinator will review these diaries at every follow-up visit to verify that they have been completed properly and consistently. If needed, the patients will be re-trained on the completion of the diary. All relevant data reported in the diaries will be translated into the eCRF by the research coordinator.

6.4.2Continuous Glucose Monitoring (CGM)

All study patients (except for the single dose patients) will receive a XXX CGM device for the entire duration of their study participation. The investigator will train the patients on how to place the CGM device and will provide written instructions to the patient. The data generated by the device will be downloaded at every site visit. The devices will store data for up to 30 days.

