8.2. Assessing Severity of Adverse Events

The severity of adverse events will be designated as mild, moderate, severe, life threatening, or fatal per National Cancer Institute (NCI) common terminology criteria for adverse events (CTCAE) version 4.0. If not specifically addressed in NCI CTCAE version 4.0, use the table below:

Mild – Grade 1	Transient or mild discomfort; requiring no limitation of activity; no therapy
Moderate – Grade 2	Mild-moderate impact on activity; requiring some assistance and medical intervention

Confidentiality Statement

Severe – Grade 3	Marked impact on activity; requiring some assistance and medical intervention	
Life Threatening – Grade 4	Complete disability; requiring significant assistance and medical intervention and/or hospitalization	
Death – Grade 5	Adverse event with fatal outcome	

The term "severe" is often used to describe the intensity (severity) of a specific event (as in mild, moderate, or severe myocardial infarction); the event itself, however, may be of relative minor medical significance (such as severe headache). This is not the same as "serious", which is based on patient/event outcome or action criteria usually associated with events that pose a threat to a patient's life or functioning. Seriousness (not severity) serves as a guide for defining regulatory reporting obligations.

8.2.1Grading of Hypoglycemic and Hyperglycemic Events

For this study of participants with type 1 diabetes, the NCI-CTCAE will not be used to grade hypoglycemia and hyperglycemia. Please refer to the grading criteria for hypoglycemic and hyperglycemic events below.

In line with the Joint Position Statement of the American Diabetes Association and the European Association for the Study of Diabetes (International Hypoglycaemia Study, 2017), events of hypoglycemia will be classified as outlined below.

- hypoglycemia Level 1: A glucose alert value of 3.9 mmol/l (70 mg/dl) or less for at least 20 minutes
- hypoglycemia Level 2: A glucose level of <3.0 mmol/l (<54 mg/dl), sufficiently low to indicate serious, clinically important hypoglycemia.
- hypoglycemia Level 3: Severe hypoglycemia, as defined by the American Diabetes Association, denoting severe cognitive impairment requiring external assistance for recovery.

Major hyperglycemic events will be defined and graded as follows:

- Grade 4 = coma or life-threatening event or event resulting in hospitalization.
- Grade 5 = death.

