- Abnormal Not Clinically Significant or
- Abnormal Clinically Significant.

For repeat dose patients the physical examination will be performed at Visit 1, 2, 5, 8, 13-19. For single dose patients the physical examination will be performed at screening, treatment and post treatment.

The frequencies (and percentage) of normal, abnormal but not clinically significant or abnormal and clinically significant will be tabulated.

Physical Examination data will be listed.

ECG

The investigator will perform a 12-lead ECG. The results will be recorded as

- Normal,
- Abnormal Not Clinically Significant or
- Abnormal Clinically Significant.

For single dose patients ECG status will be collected at screening (Visit 1) and at post treatment only if there is a suspicion of cardiac problems. For repeat dose patients ECG status will be collected at Visit 1, Visit 15, Visit 19 and in addition at Visit 17 if there is a suspicion of cardiac problems.

The frequencies (and percentage) of normal, abnormal but not clinically significant or abnormal and clinically significant will be tabulated.

ECG data will be listed.

Hypoglycemic events

Hypoglycemic events will be documented in the patient diary. Events of hypoglycemia will be classified as outlined below.

- hypoglycemia Level 1: A glucose alert value of 3.9 mmol/l (70 mg/dl) or less for at least 20 minutes
- hypoglycemia Level 2: A glucose level of <3.0 mmol/l (<54 mg/dl), sufficiently low to indicate serious, clinically important hypoglycemia.
- hypoglycemia Level 3: Severe hypoglycemia, as defined by the American Diabetes Association, denoting severe cognitive impairment requiring external assistance for recovery.

For the purposes of this study, hypoglycemia events classified as level 1 will not be recorded separately on the hypoglycemia event electronic case report form (eCRF), unless the investigator feels that the event is medically important. Hypoglycemia events level 2 and 3 will be recorded separately on the hypoglycemia event eCRF. The evaluation that produced the value or result should be repeated until that value or result returns to normal or can be explained and the participant's safety is not at risk. In addition, all hypoglycemia events meeting the definition of SAE should be recorded as serious adverse events in the eCRF.

Time of the events will be divided in the following time periods:

- Pre-treatment: all events until the day before treatment start

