- During treatment: all events reported on the day of treatment start (Day 1) and up to the last treatment day
- Post-treatment: all events reported after the last treatment day

The number of hypoglycemic events and patients with hypoglycemic events will be summarized per cohort, treatment, level and time period.

All hypoglycemic events recorded in the eCRF will be listed. Relative day to treatment start will be included in the listing.

Hyperglycemic events

Major hyperglycemic events will be defined and graded as follows:

- Grade 4 = coma or life-threatening event or event resulting in hospitalization.
- Grade 5 = death.

For this study diabetic ketoacidosis should be reported as grade 4 hyperglycemia (a single adverse event) resulting in hospitalization and/or life threatening consequences.

Hyperglycemic events will be collected and presented as SAEs with no separate tabulation. See section 6.3.9 for further details on presentation.

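### Hypoglycaemic events are to be counted over periods of very unequal length with no patient-time; as a minor point, the CGM table has no row at the 54 mg/dL Level 2 threshold

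*SAP*

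**What the plan says.** **Events.** SAP 6.3.9 states "Hypoglycemic events will be documented in the patient diary" and classes the events as Level 1, 2 or 3. It splits them into pre-treatment, treatment and post-treatment periods. The treatment period is defined as "During treatment: all events reported on the day of treatment start (Day 1) and up to the last treatment day", and the post-treatment period is everything later. The planned output is: "The number of hypoglycemic events and patients with hypoglycemic events will be summarized per cohort, treatment, level and time period". The table list in SAP 7.1 has one matching entry, a summary of hypoglycaemic events. Neither document plans patient-days or an event rate. On recording, Protocol 6.4.1 says: "The electronic diaries will be kept from the day of signing the informed consent until the patient is withdrawn or completes the study".

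**CGM.** The same SAP section lists total recording time, time from 71 to 179 mg/dL, time above 179, "Time in the low range (the time below 71 mg/dl"), "Time in the very low range (the time below 50 mg/dl") and missing time. These "will be summarized in hours/minutes and percentages of the total CGM recording time, per cohort". Protocol 8.2.1 and the SAP's own event section both define "hypoglycemia Level 2: A glucose level of <3.0 mmol/l (<54 mg/dl), sufficiently low to indicate serious, clinically important hypoglycemia".

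**The concern.** The SAP chose to split events into before, during and after treatment, so a reader will look across those columns. The columns cover very different lengths of time, and a count rises with time observed even when the risk is unchanged. The share of patients with at least one event has the same fault: a percentage corrects for the number of patients in a group, not for how long each was watched. In a descriptive study the tables are the result. Safety is the primary objective, and SAP 3.2 lists hypoglycaemic events among the secondary safety endpoints.

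The visit schedule does not supply the true denominators. The split falls at each patient's own last treatment day, and diary recording runs from consent to withdrawal or completion.

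The CGM matter is one of alignment. Two outputs in one SAP section use different low-glucose cut-offs, and neither document gives a reason for 50 mg/dL.

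**Working it through.** The plan has no figure of its own to reproduce, because the sample size is stated not to rest on statistical considerations. The check is arithmetic on period lengths, then a comparison of cut-offs.

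**1. Period lengths (repeat-dose patients who complete the schedule)**
- Pre-treatment: up to about 28 days (screening window, Protocol 7.3.1).
- Treatment: 56 days (Protocol 5.1.1).
- Post-treatment to Day 360 (Protocol 5.2.1 and 5.2.2): 360 − 56 = 304 days.
- Post-treatment if data are cut at Day 180: 180 − 56 = 124 days. SAP 6.9 places the primary analysis when all patients have passed Day 180. The cut at exactly Day 180 is my assumption; without it, patients enrolled early contribute more.

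**2. Counts at a constant rate** (expected count = rate × days / 365.25, so the rate cancels in a ratio)
- Day 180: 124 / 56 = 2.2.
- Day 360: 304 / 56 = 5.4.
- If the rate halved after treatment, the ratios would be 0.5 × 2.21 = 1.1 and 0.5 × 5.43 = 2.7. A true halving would still show as no fewer events.

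**3. Patients with at least one event** (1 − exp(−rate × days / 365.25)). The documents give no event rate, so the rates are assumed and span a wide range.

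| Assumed rate per patient-year | 56 days on treatment | 124 days after | 304 days after |
|---|---|---|---|
| 1 | 14.2% | 28.8% | 56.5% |
| 5 | 53.5% | 81.7% | 98.4% |
| 20 | 95.3% | 99.9% | 100.0% |

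The shift is large at low rates and nearly gone at 20 per patient-year, where almost every patient has an event in either period. The ratio of counts is the same at every rate. Allowing for variation between patients does not change the direction. With a gamma frailty of shape 0.5 and mean rate 1, the share is 1 − (1 + m/0.5)^(−0.5), where m is the expected count. This gives 12.5% for m = 0.153 (56 days) and 38.7% for m = 0.832 (304 days).

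**4. CGM cut-off**
- The protocol's pair of 10 mmol/L and 180 mg/dL implies a factor of 18, so 3.0 × 18 = 54 mg/dL. The Level 2 definition is internally consistent, and 50 / 18 = 2.78 mmol/L.
- Whole-number readings of 50, 51, 52 and 53 mg/dL meet the Level 2 value but appear only in the below-71 row. That row matches the Level 1 limit of 70 or less (without its 20-minute condition), so only the Level 2 cut is out of line.
- Time at 50–53 mg/dL is 1440 × [P(<54) − P(<50)] minutes per day. The documents give no glucose distribution. Assuming a mean of 140–180 mg/dL and a CV of 30–42%, it is 2.6 to 12.8 minutes per day (normal) or 0.04 to 8.6 (lognormal).

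**The case against.** **The study is descriptive, with no tests, and no before/during/after comparison is planned.** This is correct (SAP 6.4 and 6.5). Between treatment groups within one period, planned lengths are equal for repeat-dose patients, so the distortion arises only when periods are compared. That limits the consequence. It does not remove it, because the SAP itself lays the table out by period.

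**Patient-time can be recovered.** SAP 7.2 lists visit dates and AG019 treatment end dates, and the event listing carries the relative day. This shows that the fix is feasible; it is not a planned summary.

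**The size depends on the data cut and the rate.** This stands. The factor of 5.4 needs follow-up to Day 360, and the shift in patients affected fades at high rates.

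**The CGM row makes little difference.** This largely stands. A reader might infer that the SAP redefines Level 2 at 50 mg/dL, or that Level 2 events go uncounted. Neither is so: the SAP never calls the below-50 row Level 2, and its event table uses 54. A reader might also infer that a below-54 row would let diary counts be checked against the device. It would not:
- CGM is summarised as time, for the data collected at each visit, while events are counts per period.
- Level 2 has no minimum duration, so minutes do not convert to events.
- The device is placed at the Day 1 visit, so the pre-treatment period has no planned CGM counterpart.
- The device stores up to 30 days, while the visits after Day 90 are 90 days apart (Days 180, 270 and 360).

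**Conclusion.** The main point holds as a presentation weakness with a better method at hand. For repeat-dose patients at a constant event rate, the planned table would show 2.2 times (Day 180 cut) to 5.4 times (Day 360) as many events per patient after treatment as during it. The ratios assume completion of the 56 days of treatment and of follow-up to the cut. They do not describe single-dose patients, who take AG019 on one day and keep no electronic diary. The effect on the share of patients with an event depends on the unknown rate and ranges from large to almost nil.

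The CGM point holds only as an alignment with the documents' own threshold. Its numerical effect is unknown and may be negligible. The documents do not support reading it as a wrong definition or as lost events. Neither point undermines the planned counts themselves.

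**What to change.** **Events.** In SAP 6.3.9 and in the matching table of SAP 7.1, keep the planned counts. Beside them give observed patient-days and events per patient-time, by level, period, cohort and treatment group. Count patient-days from the start of diary recording to the day before Day 1, from Day 1 to the patient's last treatment day, and from the next day to withdrawal, completion or the data cut. State the data cut for the Day 180 analysis.

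**CGM.** Add a row for time below 54 mg/dL. The below-50 row may stay. A 54–70 row is optional, since for whole-number readings it is the below-71 time minus the below-54 time.

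**Cost.** SAP wording and a little programming on data already collected, with no change to study conduct.
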